### **3.1.4 Study Day 14 or Final Study Day**

Final study day is planned to be Day 14; however, patients who complete at least 10 days of treatment will have all final study day procedures performed. Patients who discontinue early, prior to Day 10, will need to complete all final study procedures except video/pH/impedance monitoring.

The final dose of study drug will be administered, based on the patient's body weight, per NICU standards.

A physical examination (including measurement of weight, length and head circumference), vital signs (blood pressure, heart rate, temperature, and respiration rate) and laboratory assessments will be performed.

This study day will include esophageal pH monitoring, intraluminal impedance monitoring, cardiorespiratory monitoring, and video monitoring for 8 hours. Every attempt should be made to schedule this monitoring at the same time of day as the baseline monitoring, to include at least 2 feeding times and to begin approximately 2 hours before dosing and end 6 hours after dosing). The patient will continue to be monitored for reflux only for a total of 18 – 24 hours.

A Physician Global Assessment of the patient's GERD-related symptoms over the last 24 hours will also be completed (see Section 4.6.6).

Assessment of AEs, concomitant medications, and SAEs will be completed.

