### **3.1.6 pH/intraluminal impedance/video monitoring**

Placement of the pH/impedance probe will be scheduled so that it coincides just prior to feeding time if possible. If necessary, a separate feeding tube may be placed beside the pH/impedance probe, through which the investigational product may be given to the patient. (See Section 3.4.2)

Esophageal pH/intraluminal impedance will be measured and recorded for a total of 18 - 24 hours using the Sandhill Scientific Insight System. A portion of this (8 hours) will be integrated with the Respironics Alice 5 Diagnostic Sleep System, and will include measurement of cardiorespiratory data such as respiration rate, heart rate, ECG and oxygen levels, as well as video, sound and movement monitoring. A synchronizing device, developed for this study, will be used to integrate the data. Video will be recorded for 8 hours (approximately) and approximately 6 hours should be considered evaluable, which is defined as having a clear image, the camera pointed at the child, and the face and upper body are visible. The 8 hours of video should ideally include at least 2 feedings and include dosing on the final study day (2 hours before and 6 hours after dosing). Every attempt should be made to collect baseline and final study day evaluations during the same time of day.

This 8 hours of data will be downloaded onto a computer and then stored on 2 duplicate sets of 2 DVDs (or equivalent media), each labelled with patient identifier information. One set of DVDs will be kept at the study site and the other will be sent to the AstraZeneca contract research organization (CRO) data management representative.

The study nurse or qualified site personnel (ie, medical or nursing staff) will prepare surveillance notes while the monitoring is occurring. Comments from the surveillance notes will be marked on the integrated system during the review process for both the baseline and final study day visits.

The site will review the video to ensure that approximately 6 hours are considered evaluable before randomization of the patient. Patients without approximately 6 hours of evaluable video at baseline will be discontinued.

Qualified site personnel will also review the 8 hours of pH/impedance data recorded during the video monitoring and mark events in the system where applicable.

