**Figure 1 Study flow chart**

**Table 1 Study summary of assessments and procedures**

Assessment/Procedure	Baseline Day -3 to Day 0	Randomization /Treatment Day 1-13	Study Completion/ Early Discontin- uation Day 14k	Safety Follow-up 14 days (+/-2 days) after final dosem
Informed consent	X			
Clinical assessment chart	X e	X e		
Medical history	X			
pH monitoring and impedance	X f		X l	
Cardiorespiratory monitoring	X		X	
Video monitoring	X f		X l	
Inclusion and exclusion criteria	X			
Vital signs a	X	X	X	X
Physical examination b	X	X i	X	X
ECG	X g			
Laboratory evaluation	X h		X	
Prior and concomitant medications	X	X	X	X
Dosing administration		X	X	
Randomization		X j		
Physician Global Assessment	X		X	
Adverse event assessment c	X	X	X	X
Serious adverse event assessment d	X	X	X	X

a Including temperature, blood pressure (BP), heart rate and respiration rate.

b Including weight, length and head circumference.

c Adverse events will be recorded from the day when the parents sign the informed consent. All ongoing AEs must be followed until resolution or until the investigator decides and documents that no further follow-up is necessary. AstraZeneca may request additional information about such AEs.

d Serious adverse events will be recorded from the day when the parents sign the informed consent.

e Baseline and final study day clinical assessment charts will be recorded during the 24 hour period before pH/impedance monitoring.

f pH/impedance/video monitoring begins once clinical assessment charts and other baseline procedures have been completed.

g Patients must have a normal ECG at baseline (historical documentation is acceptable) without clinically significant findings as deemed by the investigator.

h Stool hemocult performed at baseline only.

i Weight and length only.

j Randomization occurs on Day 1.

k Minimum of 10 days of treatment.

l Patients who discontinue early, prior to Day 10, will need to complete all final study procedures except video/pH/impedance monitoring.

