### **3.3.5 Discontinuation of patients from treatment or assessment**

#### **3.3.5.1 Criteria for discontinuation**

Patients may be discontinued from study treatment and assessments at any time. Specific reasons for discontinuing a patient from this study are:

- Voluntary discontinuation by the patient’s parent or guardian who are at any time free to discontinue their participation in the study, without prejudice to further treatment.
- Safety reasons as judged by the investigator and/or AstraZeneca
- Severe non-compliance to protocol as judged by the investigator and/or AstraZeneca
- Incorrect enrollment or randomization of the patient.
- Development of exclusion criteria.
- Patient lost to follow-up

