#### **3.3.5.2 Procedures for discontinuation**

If a patient discontinues participation or is withdrawn, the Clinical Monitor for the site must be contacted. The reason for, and date of, discontinuation for all patients from the study will be documented in source documents and the eCRF.

Parent or guardians who discontinue their child/ward should always be asked about the reason(s) for their discontinuation and about the presence of any adverse events. If possible, they should be seen and assessed by an investigator(s). Final visit procedures should be conducted. Adverse events should be followed up and any clinical assessment charts should be completed for the patient. All patients will be followed with a safety evaluation 14 days (+/- 2 days) after the final dose of study drug (Section 3.1.4).

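### As written, the early-discontinuation visit includes a dose of study drug, which conflicts with the provision for stopping treatment, including for safety

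*Protocol*

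**What the plan says.** Section 3.1.4 plans the final study day for Day 14. Infants with at least 10 days of treatment have every final-day procedure. For those who stop sooner: "Patients who discontinue early, prior to Day 10, will need to complete all final study procedures except video/pH/impedance monitoring". The sentence that follows is unconditional: "The final dose of study drug will be administered, based on the patient's body weight, per NICU standards".

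Table 1, titled "Study summary of assessments and procedures", has a single closing column headed "Study Completion/ Early Discontin- uation Day 14". The row "Dosing administration" is marked in that column and carries no footnote. Footnote l, which repeats the exemption for early stoppers, is attached only to the pH/impedance and video rows.

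Section 3.3.5.1 lets infants be discontinued from treatment at any time. Its listed reasons include "Safety reasons as judged by the investigator and/or AstraZeneca", a parent's decision, and development of an exclusion criterion. For discontinued infants, Section 3.3.5.2 says: "Final visit procedures should be conducted". It names no procedure to be left out.

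**The concern.** An infant taken off study drug is sent to a visit whose written content includes study drug. The conflict is sharpest for a safety withdrawal. It also reaches an infant withdrawn because an exclusion criterion has developed, and known or suspected hypersensitivity to esomeprazole is one of those criteria (Section 3.3.3, criterion 11). Section 3.3.5.3 sends infants enrolled in error to the same discontinuation procedures.

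What is at stake is conduct and safety in newborns. Sites work from the schedule table, and whether a withdrawn infant is dosed should not depend on staff choosing to disregard a marked box. If sites resolve the text differently, infants withdrawn for the same reason will be handled differently.

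**Working it through.** The contradiction rests on text, so the check is to set the passages side by side.

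1. **Is dosing a final-day procedure?** Yes. It is a row of Table 1 marked in the closing column, and Section 3.1.4 lists it among the events of that day. Section 3.8 adds that study personnel give the product on all study days.
2. **Does the closing column apply to early stoppers?** Yes. It is named for both groups, and footnote l would serve no purpose there if the column described completers only.
3. **Are early stoppers exempt from dosing?** No. The exemption in Section 3.1.4 covers video and pH/impedance monitoring. Footnote l covers the same items and sits on those rows only. Exceptions were therefore made row by row, and the dosing row has none.
4. **Does the discontinuation section override this?** No. Section 3.3.5.2 calls for the final visit procedures and is silent on dosing.
5. **Does this conflict with another rule?** Yes. Section 3.3.5.1 provides for stopping treatment at any time. Steps 1 to 4, followed literally, give a further dose after that decision.

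**Infants with at least 10 days of treatment.** Two situations need separating. If the final day is simply brought forward to Days 10 to 13, the dose that day may be the planned last one and there is no conflict. If the infant has been withdrawn from drug, Section 3.1.4 still calls for all final-day procedures, so the dosing question returns. The recording is also described relative to a dose: 2 + 6 = 8 hours around it. The protocol does not say how to time the recording if no dose is given.

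**Size.** The synopsis plans at least 90 infants to obtain 76 evaluable.

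- Planned non-evaluable: 90 − 76 = 14.
- As a share: 14 / 90 = 15.6%.

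No breakdown by reason is given. Under Section 6.3 an infant can also leave the ITT set by lacking a valid efficacy measurement without having stopped treatment. Early stoppers among the 14 could therefore number anywhere from 0 to 14. Infants recorded on Days 10 to 13 can be evaluable and need not be among the 14. The number withdrawn for safety cannot be estimated at all.

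**The case against.** The strongest reply is that stopping treatment is what discontinuation means. Section 3.3.5 is about discontinuation from treatment or assessment; Section 3.3.5.2 speaks of reasons, adverse events, charts and follow-up, and never of dosing. Section 3.1.5 refers to the final dose for discontinued and completed infants alike, which reads naturally as whichever dose came last. The Table 1 column is labelled Day 14 with a footnote on a minimum of 10 days of treatment, so its dosing mark may have been written with completers in mind. Most sites would probably not dose a withdrawn infant. That is a fair prediction of behaviour, but it remains an inference: Section 3.1.4 and Table 1 each say otherwise, and no passage states the exception.

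Three stronger readings are tempting, and the documents do not support them.

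- *A reader might infer that the final recording cannot be made for infants withdrawn on Days 10 to 13.* Section 3.1.6 asks the video to "include dosing on the final study day (2 hours before and 6 hours after dosing"), but introduces this as an ideal. Section 3.1.4 uses the language of best effort and approximation. Section 4.6.2 states the window more flatly, though still for roughly 8 hours. All three sections also ask for the same time of day as baseline, and the baseline recording itself precedes any dosing. The gap is an unstated timing rule; the recording remains possible.
- *A reader might infer that a shifted last-dose date distorts the safety data.* Sections 3.1.5 and 3.3.5.2 time follow-up at 14 days (± 2) after the final dose. If a further dose were given, counting from it would be consistent with that rule, and Section 3.7 already requires every administration to be recorded. No distortion is shown.
- *A reader might take most of the 14 planned non-evaluable infants to be early stoppers.* Nothing in the protocol says why those 14 are expected to be lost.

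**Conclusion.** The point holds as a contradiction in the wording. Taken literally, Section 3.1.4, Table 1 and Section 3.3.5.2 call for a dose at the closing visit of an infant who stopped before Day 10, against Section 3.3.5.1. A smaller gap affects infants withdrawn from drug after at least 10 days, for whom the timing of the 8-hour recording is not stated if no dose is given.

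The conclusion depends on no assumed rate, effect or variance. The only assumption is that a site may follow the schedule as printed. The sample size and the primary analysis model are unaffected. The number of infants concerned is unknown: 0 to 14 of the planned non-evaluable infants, plus possibly some stopping on Days 10 to 13 who are not in that count. It should be corrected because it bears on patient safety and costs very little.

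**What to change.** Reconcile Sections 3.1.4, 3.3.5.1, 3.3.5.2 and the Table 1 dosing row:

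- Split the closing column of Table 1 into study completion and early discontinuation, or add a footnote to the dosing row. Either should state whether the final-day dose applies to an infant already withdrawn from study drug.
- Put the same statement in Sections 3.1.4 and 3.3.5.2.
- For infants withdrawn from drug after at least 10 days, state how the 8-hour recording is timed if no dose is given that day. Matching the baseline time of day is already a stated target and can serve as the reference.

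Which clinical rule applies is for the sponsor's physicians to decide; the request here is only that the passages agree. The cost is protocol wording and one table column or footnote, with no new procedure or data field.

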### **3.1.5 Safety Follow-up**

Following administration of the final dose of study drug, all patients (discontinued or completed) will have a safety follow-up evaluation performed as in-patient or office visit. The safety follow up visit will occur 14 days (+/- 2days) after final dose.

This visit will include evaluation vital signs, and physical exam.

Adverse events (AEs), concomitant medications, and serious adverse events (SAEs) will be documented. All ongoing AEs must be followed until resolution or until the investigator decides and documents that no further follow-up is necessary. AstraZeneca may request additional information about such AEs.

### **3.1.6 pH/intraluminal impedance/video monitoring**

Placement of the pH/impedance probe will be scheduled so that it coincides just prior to feeding time if possible. If necessary, a separate feeding tube may be placed beside the pH/impedance probe, through which the investigational product may be given to the patient. (See Section 3.4.2)

Esophageal pH/intraluminal impedance will be measured and recorded for a total of 18 - 24 hours using the Sandhill Scientific Insight System. A portion of this (8 hours) will be integrated with the Respironics Alice 5 Diagnostic Sleep System, and will include measurement of cardiorespiratory data such as respiration rate, heart rate, ECG and oxygen levels, as well as video, sound and movement monitoring. A synchronizing device, developed for this study, will be used to integrate the data. Video will be recorded for 8 hours (approximately) and approximately 6 hours should be considered evaluable, which is defined as having a clear image, the camera pointed at the child, and the face and upper body are visible. The 8 hours of video should ideally include at least 2 feedings and include dosing on the final study day (2 hours before and 6 hours after dosing). Every attempt should be made to collect baseline and final study day evaluations during the same time of day.

This 8 hours of data will be downloaded onto a computer and then stored on 2 duplicate sets of 2 DVDs (or equivalent media), each labelled with patient identifier information. One set of DVDs will be kept at the study site and the other will be sent to the AstraZeneca contract research organization (CRO) data management representative.

The study nurse or qualified site personnel (ie, medical or nursing staff) will prepare surveillance notes while the monitoring is occurring. Comments from the surveillance notes will be marked on the integrated system during the review process for both the baseline and final study day visits.

The site will review the video to ensure that approximately 6 hours are considered evaluable before randomization of the patient. Patients without approximately 6 hours of evaluable video at baseline will be discontinued.

Qualified site personnel will also review the 8 hours of pH/impedance data recorded during the video monitoring and mark events in the system where applicable.

A qualified reader, (either a central reader or site specific as applicable) per standard guidelines, will review the 8 hours of all the integrated data (cardiorespiratory monitoring, pH, impedance and video) and document any correlations between the events and the presence of reflux. The start and stop time of events will be determined so that durations can be calculated. The reader who will be reviewing the integrated data, as well as all site personnel, will be blinded to the investigational product assigned to the patient.

The 18 – 24 hour pH/impedance data will be used to calculate the reflux index in those patients that complete this procedure. However, as long as patients have completed the 8 hours of video monitoring, they will be considered evaluable regardless of whether they complete the remaining pH/impedance monitoring.

The following assessments of all types of reflux episodes (acid or non-acid) will be made at baseline and after treatment using standard reports from the pH/intraluminal impedance monitoring:

[figure not shown]
- acidic GER episodes (pH<4)

- weakly acidic GER episodes (pH 4 – 6.9)
- non acidic GER episodes (pH $\geq$ 7)
- liquid GER episodes
- mixed gas/liquid GER episodes
- mean bolus clearance time
- mean acid clearance time

The following assessments of acidic reflux episodes will be made at baseline and after treatment using the standard reports from the esophageal pH probe based on the entire time of pH monitoring:

- number of acidic reflux episodes (pH<4)
- number of acidic reflux episodes greater than 5 minutes
- % time pH < 4
- % time pH 4 – 6.9

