## **4. MEASUREMENTS OF STUDY VARIABLES AND DEFINITIONS OF OUTCOME VARIABLES**

### **4.1 Primary variable**

The primary variable is change from baseline in the number of occurrences of symptoms of GERD, as observed from video recording, and GERD-related signs detected from cardiorespiratory monitoring.

- For other efficacy variables, see [Table 3](#).

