##### **4.6.2.1 Method of Assessment**

A qualified reader will review per standard guidelines the video and determine the presence or absence of symptomatic episodes in the images in conjunction with pH/impedance monitoring and other measurements.

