##### **4.6.2.2 Calculation or derivation of outcome variables**

The qualified reader will determine if each event recorded in the integrated video/pH/impedance data (those which were marked either through the surveillance notes of the site staff or the review of the pH/impedance data) is related to reflux and if they are, whether the event is acidic, weakly acidic or non acidic from the pH data and nature of the event (liquid or mixed liquid/gas reflux) from the impedance data. Events to be evaluated include the neuro-behavioral variables:

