### **6.2 Description of outcome variables in relation to objectives and hypotheses**

The primary objective of this study is to evaluate if there is a difference between esomeprazole and placebo in the treatment of signs and symptoms of GERD as observed in an 8-hour video recording along with cardiorespiratory monitoring. Video, pH/impedance, and cardiorespiratory monitoring will occur at baseline (before treatment) and the final study day. Symptoms or symptomatic reflux episodes of GERD will be determined by a qualified reader, in a blinded fashion, by review of the video recording, the pH/impedance monitoring, and the cardiorespiratory monitoring. Other variables can be found in [Table 3](#).

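### The reader judges the video symptoms in the primary count with the pH/impedance trace in view, which may partly unblind the judgement-based part of the endpoint

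*Protocol*

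**What the plan says.** **Endpoint.** Protocol 4.1: "The primary variable is change from baseline in the number of occurrences of symptoms of GERD, as observed from video recording", together with signs from cardiorespiratory monitoring. Table 3 and 6.4 define it the same way. Linkage to reflux on pH/impedance belongs to a separate secondary variable in Table 3.

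**Read.** Protocol 3.1.6 says that a qualified reader "will review the 8 hours of all the integrated data (cardiorespiratory monitoring, pH, impedance and video") and documents how events correlate with reflux. Protocol 4.6.2.1 asks the reader to "determine the presence or absence of symptomatic episodes in the images in conjunction with pH/impedance monitoring and other measurements". Protocol 6.2 treats symptoms and symptomatic reflux episodes in one sentence; both are determined "in a blinded fashion, by review of the video recording, the pH/impedance monitoring, and the cardiorespiratory monitoring".

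**Marking.** Protocol 3.1.6: "Qualified site personnel will also review the 8 hours of pH/impedance data recorded during the video monitoring and mark events" where applicable. Protocol 4.6.2.2 describes the events that the reader judges as "those which were marked either through the surveillance notes of the site staff or the review of the pH/impedance data". The list that follows in 4.6.2.2 includes gagging, back arching and irritability/crying/fussing.

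**Blinding.** Protocol 3.1.6 states that the reader and all site personnel do not know the assigned product, and 3.6.1 that active and placebo vials look the same. No section provides for a masked pH channel, or for scoring the video before the pH/impedance data are shown.

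**The concern.** The prescribed read does not match the endpoint. pH/impedance is outside the definition of the primary count but inside the procedure that produces it.

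This matters because of what the drug does. Protocol 1.2 says that proton pump inhibitors reduce the acidity of refluxate in older children and adults, and 2.2 makes fewer acidic reflux episodes a secondary objective. A reader who sees the pH trace, and who under 4.6.2.2 classifies reflux-related events by acidity, may form a view of the arm without ever seeing the code. Identical vials do not protect against that.

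Back arching, gagging and fussing are judged by eye, so a reader's expectation could move the count. The baseline covariate in the ANCOVA would not remove such a shift, because it would arise at the post-treatment read.

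A second, weaker route is event selection. If 4.6.2.2 means that only marked moments are evaluated, treatment might affect which moments are examined.

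**Working it through.** **1. The passages side by side**

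| Element | Primary variable (4.1, Table 3, 6.4) | Procedure (3.1.6, 4.6.2.1, 4.6.2.2, 6.2) |
|---|---|---|
| Video | included | reviewed |
| Cardiorespiratory | included | reviewed |
| pH/impedance | not included | reviewed, used in judging presence of symptoms, and one source of event marks |

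The 3.1.6 sentence alone shows only that the reader sees the pH data, and its stated purpose is reflux correlation. The decisive text is 4.6.2.1, which applies the joint view to whether a symptom is present at all.

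**2. The plan's own sample size**

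Inputs from Protocol 6.5: SD = 1.5 × difference, alpha 0.05, power at least 80%, 38 per group. Sidedness is not stated; two-sided is assumed (one-sided gives 28 per group and does not fit).

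n per group = 2 × (1.960 + 0.842)² × 1.5² = 2 × 7.85 × 2.25 ≈ 35.3, so 36. The t-test version gives 36.3, so 37. Power at 38 per group is 82.8% (normal) or 81.8% (t). The planned 38 is consistent with its stated aim. The planned difference is 1/1.5 = 0.667 SD.

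**3. Sensitivity to an assumed shift**

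Suppose there is no true drug effect, but the read shifts the between-arm difference by b × SD. With 38 per arm the standard error of the difference is √(2/38) = 0.2294 SD. The two-sided rejection probability is then

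Φ(b/0.2294 − 1.96) + Φ(−b/0.2294 − 1.96).

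| Assumed b (SD) | Share of planned difference (b × 1.5) | b/0.2294 | Type I error, normal | Type I error, t-test |
|---|---|---|---|---|
| 0.1 | 15% | 0.436 | 0.072 | 0.0715 |
| 0.2 | 30% | 0.872 | 0.1406 | 0.1382 |
| 0.3 | 45% | 1.308 | 0.2576 | 0.2522 |

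The values of b are assumptions; nothing in the protocol fixes them.

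**The case against.** Several points on the other side are sound.

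- **The integrated read is needed.** The reflux-associated and weakly acidic endpoints cannot be scored without pH/impedance. This stands, so the defect is the lack of separation for the primary count, not the integrated read itself.
- **Unseen reading rules.** Reading follows standard guidelines that are not shown and might set an order. To cure the problem, though, they would have to depart from what 4.6.2.1 says.
- **Objective components.** Apnea, bradycardia and desaturation have numeric thresholds in 4.6.3.2, so only part of the primary count is open to reader judgement. This stands.
- **Strength of the hint.** A reader might infer from the acid inhibition of more than 80% in Appendix C, 3.4 that the trace reveals the arm. The documents do not support that. The figure supports a minimum effective dose criterion for adults and is not an esophageal pH result in neonates. Protocol 1.2 calls efficacy poorly studied in infants, and Appendix C, 4.3.4 warns that efficacy may not follow from PK/PD data alone. The trace may hint at the arm; no more can be said.
- **Event selection.** A reader might infer that fewer acid events means fewer flagged moments, and so fewer counted symptoms. That chain is not established. Protocol 3.2.1 notes that impedance picks up reflux whatever its pH, so an episode that becomes weakly acidic can still be marked. Surveillance notes are a second source of marks. No section says that unmarked video symptoms go uncounted, and 4.6.2.2 can be read as addressing only reflux association.
- **Physician Global Assessment.** A reader might infer that the staff who review the trace also complete this assessment. The protocol assigns it to investigators (4.6.6) and the marking to qualified site personnel (3.1.6). It does not say that they are the same people, or which task comes first.

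**Conclusion.** The point holds as a risk of partial unblinding in the judgement-based video symptoms. It rests on the mismatch between 4.1 and 4.6.2.1, with 3.1.6 and 6.2 in support. Selection of events through marking is a possible additional route under one reading of 4.6.2.2, limited by impedance detection and by the surveillance notes.

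The documents do not show that bias will occur, and its size cannot be derived from them. A shift towards esomeprazole is the plausible direction but is an inference. The error rates of about 7%, 14% and 25% show only how sensitive the test at 38 per arm would be to assumed shifts of 0.1, 0.2 and 0.3 SD. They should not be read as the trial's actual type I error. They assume a two-sided comparison, no true effect and a uniform shift in SD units.

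It is still worth correcting before reading begins: the change is cheap, and reanalysing counts scored only with pH/impedance in view could not restore an independent read.

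**What to change.** Amend Protocol 3.1.6, 4.6.2.1 and 4.6.2.2 to specify two passes by the same reader, and align the sentence in 6.2.

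1. **First pass.** Score the full evaluable video and the cardiorespiratory channels, not only marked moments, with the pH/impedance channels and all marks derived from them hidden. Lock the primary counts.
2. **Second pass.** Open pH/impedance and assign reflux association and acidity for the secondary endpoints, without changing the locked counts.

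As a precaution, record the final-day Physician Global Assessment before the assessing investigator sees the final pH/impedance data.

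The cost is protocol and reader-guideline wording plus extra reading time per recording. No additional patients, recordings or readers are needed, and the sample size is unaffected. The fix assumes that the integrated system can hide channels and marks, which the documents do not state and the sponsor should confirm.
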